**Table 12: Estimated Power to Detect the Mean Differences in Maternal Growth Outcomes**  
**Maternal DXA, Whole Body Bone Mineral Content (BMC) (g)**  
**(Mean=0.979, SD=0.111)\*\***

BMD	Difference to be Detected	Effect Size (SD*)	Power (based on sample sizes**)		
			N1=200 N2=100	N1=180 N2=90	N1=160 N2=80
Lumbar Spine	1% (of 0.979*)	0.0098 (0.111*)	11%	10%	10%
	2%	0.0196	30%	28%	25%
	3%	0.0294	58%	53%	49%
	4%	0.0392	82%	78%	73%
	5%	0.0490	95%	93%	89%
	6%	0.0587	99%	98%	97%
	0.10*SD	0.0111	13%	12%	11%
	0.15*SD	0.0167	23%	21%	19%
	0.20*SD	0.0222	37%	34%	31%
	0.25*SD	0.0278	53%	49%	44%
	0.30*SD	0.0333	69%	64%	59%
	0.35*SD	0.0389	81%	77%	72%
	0.40*SD	0.0444	90%	87%	83%
Total Hip	1% (of 0.968*)	0.0097 (0.119*)	10%	10%	9%
	2%	0.0194	26%	24%	22%
	3%	0.0290	51%	47%	43%
	4%	0.0387	75%	71%	66%
	5%	0.0484	91%	88%	84%
	6%	0.0581	98%	97%	94%
	0.10*SD	0.0119	13%	12%	11%
	0.15*SD	0.0179	23%	21%	19%
	0.20*SD	0.0238	37%	34%	31%
	0.25*SD	0.0298	53%	49%	44%
	0.30*SD	0.0357	68%	64%	59%
	0.35*SD	0.0417	81%	77%	72%
	0.40*SD	0.0476	90%	87%	83%

\*Data were from JAIDS (Mirembe, 2015): mean (SD) = 0.979 (0.111) for lumbar spine; mean (SD) = 0.968 (0.119) for total hip.

\*\*Sample Sizes: N1 -- PrEP Arm, N2 -- non-PrEP Arm

## 9.2.5 Monitoring – PrEP Comparison Component

Since this study is not randomized, some potential concerns are differential enrollment into the two cohorts, either by country, gestational period of enrollment, or in the proportion of women in the youngest age group (16-17 years old). Large differences in cohort enrollment – by country, age or by gestational period of enrollment could introduce bias or make some analyses no longer feasible. To manage those potential risks, the balance between Cohorts 1 and 2 during enrollment at each site will be monitored by the CMC and active measures undertaken to minimize such biases. The accruals and updated status of women in Cohort 1 and Cohort 2 will be closely monitored and reported regularly to participating sites for each site and across all sites to guide

the recruitment strategies. If the CMC observes significant divergence between cohorts in these enrollment characteristics then the team will discuss and agree on plans for notifying sites to adopt remedial measures, which may include curtailing enrollment to the Cohort more commonly chosen while enrollment into the other Cohort proceeds.

## 9.2.6 Analyses-PrEP Comparison Component

The primary analyses to address the objectives of the PrEP Comparison Component are outlined below. For a more detailed description of the analyses to be conducted, please refer to the Statistical Analysis Plan.

### Descriptive summaries:

Entry demographic, pregnancy, pregnancy history, psychosocial, sexual behavior and partner characteristics of women in Cohort 1 and women in Cohort 2 will be summarized and compared using chi square tests (or Fishers exact test as appropriate) for discrete variables and t tests or Wilcoxon rank sum tests for continuous variables. Logistic regression models will be fit to identify predictors of PrEP initiation.

### Primary Objective 2.3.1:

- Women in Cohort 1 will comprise the analysis sample. A binary indicator, “optimal adherence” will be created, as defined above as TFV-DP levels in DBS meeting or exceeding the threshold determined in the PK Component as corresponding to protective levels of PrEP (24). At each visit that TFV-DP levels are obtained (see [Appendix IIA](#)), the proportion of women with optimal adherence will be calculated based on their TFV-DP levels at each visit. The proportion of visits with optimal adherence in the pregnancy vs. postpartum periods will be calculated and compared.
- Exploratory analyses identifying baseline and time-varying predictors of optimal adherence will be conducted with multivariable regression models using generalized estimating equations with a logistic link (to account for repeated measures across time for each participant).
- Adherence (as measured in TFV-DP levels) will also be summarized as a continuous outcome (median, IQR and mean [SD]) at each time point noted above when drug levels are measured, and “average” adherence across pregnancy and postpartum periods, will be calculated, using generalized estimating equations. We will focus on periods during which the participant has formally elected to be on PrEP. If a woman elects to formally stop PrEP (by notifying study personnel), periods of being formally off study drug will not be considered in adherence calculations.
- Other approaches to summarizing the adherence outcome will be considered. This includes an ordinal variable with categories corresponding to different dosing levels. For this type of outcome, at each visit that drug levels are measured in DBS, descriptive analyses will summarize the proportion of women in each adherence category, refer to categories discussed in [Section 9.1.6](#).

- Baseline characteristics, and patterns of adherence and duration on PrEP will be summarized separately for women in Cohort 2 who later decide to initiate PrEP using the approaches outlined above.
- The following additional descriptive statistics will be calculated: The proportion of women a) with at least one visit with TFV-DP levels corresponding to optimal adherence, b) who had TFV-DP levels corresponding to optimal adherence at all visits, c) who had no detectable TFV-DP levels at any visit.

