### 1.3.3.1 PK Component Results

The PK Component evaluated PK characteristics of daily oral PrEP (FTC 200mg/TDF 300mg) among 20 pregnant (median gestational age: 18 weeks) and 20 postpartum (median time after delivery: 7 weeks) women at a median age of 20 years. Daily FTC/TDF was administered under direct observation for 12 weeks; of 3360 doses, 3352 [>99%] were directly observed). Weekly TFV-DP was measured from DBS using a validated liquid chromatography-tandem mass spectrometry assay. TFV-DP distributions were determined at 12 weeks and groups compared with the Wilcoxon test. Population PK models were fit to estimate half-life and steady state concentrations.

TFV-DP accumulated with a half-life of 15.3 days (95%CI: 12.8,17.8) in pregnancy and 18.0 days (95%CI: 15.3,20.7) postpartum, with steady state achieved by 8-10 weeks in both groups. Median TFV-DP was 965 fmol/punch (IQR: 691,1166) in pregnancy vs 1406 fmol/punch (IQR: 1053,1859) postpartum (p=0.006). Predicted median TFV-DP was 890 fmol/punch (IQR: 704,1143) in pregnancy vs 1418 fmol/punch (IQR: 1179,2139) postpartum. Under conditions of near perfect adherence, TFV-DP concentrations in DBS were approximately one-third lower in pregnancy compared to postpartum. TFV-DP levels in DBS observed in pregnancy also appeared lower than those reported in analogous studies of men and non-pregnant, non-lactating women in the US(167, 168).

These results confirm previous findings (see [Section 1.3.2](#)) that suggested drug levels in pregnant women may be lower than in a non-pregnant population. The PK Component results do not, however, provide information about PrEP efficacy among pregnant women, and data about the adherence-efficacy relationship during pregnancy remain limited.

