### 9.1.6 Analysis-PK Component

Prior to conducting analyses for the PK Component, the CMC (to include a minimum of the Protocol Epidemiologist and/or Statistician and the Pharmacologist), will review the pattern of completeness of each maternal participant's TFV-DP concentration data to determine suitability for inclusion in the analysis. Weekly TFV-DP concentration levels in DBS will be plotted for each maternal participant. In each of the two groups (antepartum and postpartum groups), the distributions of steady state concentration (Css) defined as the TFV-DP concentration observed at Week 12 corresponding to 6-7 day/week adherence ("excellent adherence"), will be summarized. Estimates of median, IQR, mean, standard deviation, and 95% confidence intervals will be calculated for each of the two groups. Differences in mean Css between the antepartum and postpartum groups will be evaluated using two sample t tests.

Estimated concentrations corresponding to numbers of doses/week (or percentages of doses taken) in the antepartum and postpartum periods will be derived from the two measures above (antepartum Css and postpartum Css after 12 weeks of daily dosing), assuming dose proportionality (in cases that doses were missed). The drug threshold corresponding to “excellent adherence” will be defined as TFV-DP levels meeting or exceeding the 25th percentile of the distribution of TFV-DP concentrations at Week 12 of the PK Component. “Excellent adherence” is defined as the TFV-DP concentration corresponding to 6/7 doses per week on average, based on Cottrell et al who modeled that at least 6/7 doses per week is needed for adequate drug concentrations in women. The PK testing laboratory will provide sites with a drug level result and reference ranges as it relates to the categorized level of adherence to use during adherence counselling sessions (24). The reference ranges will include approximately three adherence categories, aligned with other similar studies in the field. For example, excellent adherence (equivalent to six to seven doses per week), good adherence with room for improvement (four to five doses per week), poor adherence (one to three doses per week), and not taking any doses (undetected TFV-DP levels).

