
 • Failure to start PrEP (in Cohort I or Cohort 2/Step 2) (Treatment policy strategy) • Discontinuation of PrEP: Only visits occurring prior to discontinuation of PrEP will be included. (While on treatment strategy) • HIV seroconversion: Only visits occurring up to the later of the date of first positive HIV test or date when PrEP is discontinued will be included. (While on treatment strategy) 	
Missing data could occur in the following situations:
 
 • Missing visit(s) when adherence would have been assessed • Missing drug concentration results due to sample collection or processing issues. 
Visits without adherence data will be excluded. Sensitivity analyses will be conducted imputing "suboptimal adherence" for each missed visit/concentration result

Population-level summary measure	Analysis approach

 1. Probability of optimal adherence according to TFV-DP levels in DBS at defined times during pregnancy and postpartum 2. Probability of optimal adherence while pregnant and up to 26 weeks postpartum 	
 1. At each visit that TFV-DP levels are obtained, the binomial proportion of women with optimal adherence will be calculated bounded by an exact (Clopper-Pearson) 95% confidence interval. 2. The binomial proportion of visits with optimal adherence in pregnancy and postpartum periods during periods when women are

	formally prescribed PrEP will be calculated with exact (Clopper-Pearson) 95% confidence intervals.
--	--

Supplemental Analyses:

- Exploratory longitudinal analyses identifying baseline and time-varying predictors of optimal adherence will be conducted with multivariable regression models which account for repeated measures across time for each participant.
- Adherence (as measured in TFV-DP levels) will also be summarized as a continuous outcome measure (median, IQR and mean [SD]) at each time point noted above when drug levels are measured, and “average” drug concentrations across pregnancy and postpartum periods, will be calculated, using generalized estimating equations as appropriate. Log transformation of this outcome will be considered if the distribution is not normal.

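### The supplemental continuous adherence summary averages raw TFV-DP across pregnancy and postpartum, although the same daily dosing gives about 46-59% higher levels postpartum

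*Protocol*

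**What the plan says.** Protocol 9.2.6, under Primary Objective 2.3.1, introduces the continuous outcome with: "Adherence (as measured in TFV-DP levels) will also be summarized as a continuous outcome (median, IQR and mean [SD]) at each time point". The same sentence adds that average "adherence across pregnancy and postpartum periods, will be calculated, using generalized estimating equations". It mentions no adjustment for pregnancy status or time on PrEP.

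SAP 6.3.1 places this under Supplemental Analyses. The sentence still opens by calling TFV-DP levels adherence, but the quantity averaged is now "drug concentrations across pregnancy and postpartum periods, will be calculated, using generalized estimating equations as appropriate". The only modification offered is a log transformation if the distribution is not normal.

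Protocol 1.3.3.1 reports the PK Component results. On dosing: "of 3360 doses, 3352 [>99%] were directly observed". On observed levels: "Median TFV-DP was 965 fmol/punch (IQR: 691,1166) in pregnancy vs 1406 fmol/punch (IQR: 1053,1859) postpartum (p=0.006"). On modelled levels: "Predicted median TFV-DP was 890 fmol/punch (IQR: 704,1143) in pregnancy vs 1418 fmol/punch (IQR: 1179,2139) postpartum". The protocol's own summary is that "TFV-DP concentrations in DBS were approximately one-third lower in pregnancy compared to postpartum".

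The main adherence estimand in SAP 6.3.1 is binary. The optimal-adherence cut-offs are 600 fmol/punch (up to 6 weeks on PrEP) and 650 (beyond 6 weeks) in pregnancy, and 700 and 1050 when not pregnant. The colour zones in the SAP appendix follow the same split.

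**The concern.** A continuous adherence measure should move when pill-taking moves and stay still when it does not. Raw TFV-DP fails this test across delivery, because the level produced by a given number of tablets differs between pregnancy and postpartum. It also fails early in treatment, because the drug is still accumulating at Week 4. A log transformation does not help: a multiplicative shift becomes an additive one of the same meaning.

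The plan recognises this elsewhere. The binary cut-offs and colour zones are set by pregnancy status and time on PrEP, and only the continuous summary ignores both. Whether adherence holds up after delivery is central to objective 2.3.1. A table headed adherence that rises postpartum, beside a binary result that falls, would invite a wrong reading of the study.

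**Working it through.** **Inputs.** Week 12 medians under observed daily dosing: 965 and 1406 observed, 890 and 1418 predicted (Protocol 1.3.3.1). Half-lives: 15.3 days in pregnancy, 18.0 days postpartum (same section). Accumulation model: C(t) = Css × (1 − e^(−Kt)), with K = ln2 / half-life (Protocol 10.2). Dose-to-level relation: Protocol 9.1.6 derives levels by dose "assuming dose proportionality (in cases that doses were missed").

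**1. The plan's own figure.** 1 − 965/1406 = 31.4% and 1 − 890/1418 = 37.2% lower in pregnancy. Both fit the protocol's one-third. Inverted, 1406/965 = 1.46 and 1418/890 = 1.59.

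**2. Dosing change that leaves the raw level flat at steady state.** 7 × 965/1406 = 4.8 doses a week; 7 × 890/1418 = 4.4 doses a week.

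**3. Visit averages with unchanged daily dosing.** In pregnancy the fraction of steady state at week w is 1 − 0.5^(7w/15.3): 0.719, 0.921 and 0.978 at Weeks 4, 8 and 12. On the observed median this gives 694, 889 and 944, mean 842. Adding Week 24 and Labor and Delivery (both about 965) gives a mean of 891.

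Postpartum, the level moves from 965 towards 1406 with an 18-day half-life. The fraction of the gap still open is 0.5^(7w/18): 0.198 at Week 6, 0.023 at Week 14 and 0.001 at Week 26. The levels are 1318, 1396 and 1406, mean 1373.

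| Medians | Antepartum visits | Pregnancy mean | Postpartum mean | Apparent rise |
|---|---|---|---|---|
| Observed | 4, 8, 12 | 842 | 1373 | 63% |
| Observed | 4, 8, 12, 24, L&D | 891 | 1373 | 54% |
| Predicted | 4, 8, 12 | 776 | 1379 | 78% |
| Predicted | 4, 8, 12, 24, L&D | 822 | 1379 | 68% |

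**4. Visit averages when dosing falls from 7 to 4 a week at delivery.** The postpartum target is 1406 × 4/7 = 803. The levels are 835, 807 and 804, mean 815. Against 842 or 891 in pregnancy this is a change of −3% or −8%, for a 43% cut in tablets. On predicted medians the postpartum mean is 816, against 776 or 822 (+5% or −1%).

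**5. What the binary measure shows.** Assume lognormal levels with log-SD = ln(Q3/Q1)/(2 × 0.6745), which is 0.388 in pregnancy and 0.421 postpartum. At 7 doses a week in pregnancy, about 85% of women are at or above 650. Postpartum, about 76% are at or above 1050 at 7 doses a week and about 42% at 4.8. The fall is visible.

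**6. After rescaling.** As a percentage of the expected daily-dosing level for the same period, the fall that was invisible in step 2 becomes 100% to 69% (observed medians) or 100% to 63% (predicted).

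**The case against.** The strongest reply concerns scope. The SAP makes this summary supplemental and renames the average as drug concentrations. Its overview of the final report lists the number and percentage with optimal adherence and the missed adherence visits, with no mean TFV-DP, although detail is left to the Analysis Implementation Plan. Neither document prescribes a pregnancy-versus-postpartum comparison of raw levels, and the averaging phrase could mean one average per period. All of this stands and limits the weight of the point. It does not remove it: the lead-in still says adherence, and two period averages invite the same comparison as a pooled one.

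A reader might infer that the trial's adherence result would miss a postpartum decline. The documents do not support that, because the primary estimand and the colour zones use cut-offs for each state. A reader might also infer that the by-visit medians and means are faulty. They are not: each visit is summarised separately, and only the label needs care.

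Two cautions on size also stand. The apparent rise depends on which antepartum visits enter, so no single figure should be quoted. The ratio compares two separate groups of 20 women, and Group 2 enrolled 6-12 weeks after delivery, so the within-woman ratio soon after delivery is not measured.

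Finally, converting levels to doses per week with an early-postpartum correction would claim more than Group 2 supports. Under near-complete dosing, the observed interquartile ranges would convert to 5.0-8.5 doses a week in pregnancy and 5.2-9.3 postpartum.

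**Conclusion.** The point holds for the supplemental continuous summary only. Read as adherence, the GEE average of raw TFV-DP would rise by roughly 50-80% after delivery with no change in dosing, and at steady state would stay flat if dosing fell from 7 to about 4.4-4.8 doses a week. The main adherence result is not affected.

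The steady-state ratios rest directly on the reported medians. The dose equivalence rests on the protocol's assumption of dose proportionality. The visit averages further assume first-order accumulation at the reported half-lives and postpartum kinetics from the day of delivery. These assumptions affect the size of the distortion; its direction follows from the PK Component result. The change is worth making because it is cheap and prevents a supplemental table from appearing to contradict the primary one.

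**What to change.** In SAP 6.3.1:

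- Do not pool raw TFV-DP across delivery as adherence. Report the GEE mean separately for pregnancy and postpartum, labelled as drug concentration.
- For any continuous adherence summary that spans or compares the two periods, first express each value as a percentage of the PK Component's expected daily-dosing level for the same state and weeks on PrEP.
- Flag postpartum Week 6 as transitional, since about 20% of the pregnancy-to-postpartum gap remains at an 18-day half-life. Do not model a correction for it.
- Keep the by-visit raw tables, labelled as concentrations.

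The cost is a few lines of SAP text and one derived variable from PK data and a population model already in hand. The downside is small. The reference values come from 20 women per group, and the scale assumes dose proportionality, as Protocol 9.1.6 already does. If the reference is the median, about half of fully dosed women will exceed 100%, so the scale suits group summaries rather than individual classification.

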#### **Primary Objective 2.3.2:**

*Analyses of adverse pregnancy outcomes:* The proportion of women in Cohort 1 and Cohort 2 with adverse pregnancy outcomes (a composite indicator defined as at least one of the following: spontaneous abortion (occurring at <20 weeks gestation), stillbirth (occurring at  $\geq 20$  weeks gestation), preterm delivery (<37 completed weeks gestation), or small for gestational age (<10th percentile using INTERGROWTH-21st norms and ultrasound (US)- derived gestational age at delivery) will be estimated and compared. Univariable and multivariable logistic regression methods will be used to evaluate associations of PrEP use and the composite outcome indicating presence vs. absence of any adverse pregnancy outcomes, controlling for potential confounders. The same analyses will be conducted for each of the pregnancy outcomes which comprise the composite outcome separately.

*Analyses of maternal adverse events and infant adverse events:* Cumulative rates of maternal adverse events and infant adverse events will be compared, respectively, in Cohort 1 and Cohort 2. Where appropriate, there will be stratification according to time period (i.e., antepartum (AP) and postpartum (PP), and within AP by gestational age category of enrollment). Maternal adverse events will be considered separately from infant adverse events. Cox proportional hazards regression will be used to evaluate differences in the rate of adverse events in the two cohorts. For the maternal adverse events, among women in Cohort 1, person time will begin accruing when PrEP is initiated and for women in Cohort 2 it will begin accruing after study entry. Rates of maternal and infant adverse events in AP and PP periods will also be calculated and compared across levels of PrEP adherence (based on TFV-DP levels in DBS). Models will be fit adjusting for potential confounders.

*Analyses of infant safety outcomes re: bone health and creatinine clearance:* To address Primary Objective 2.3.2, to evaluate infant safety outcomes, (CrCl measured by Schwartz equation at birth and 26 weeks anthropometric growth measures at birth and 26 weeks, bone mineral content measured by dual energy X-ray absorptiometry (DXA) at birth and 26 weeks), mean length-for-age z-scores for the growth parameters and mean grams for BMC will be calculated, and means will be compared between infants in Cohort 1 and infants in Cohort 2 using two sample t-tests at each time point of evaluation. If normality assumptions are not met the Wilcoxon Rank Sum test will be used to evaluate differences in these endpoints by Cohort.

#### **Other Objective 2.4.1:**

Exploratory analyses will be conducted to identify individual, social, and structural barriers and facilitators to PrEP uptake during pregnancy, and to adherence and continued use during pregnancy and breastfeeding. Women in both cohorts (Cohort 1 and Cohort 2) will be included in analyses of predictors of PrEP uptake at enrollment. Logistic regression methods will be used to evaluate univariate and multivariate associations of baseline demographic, psychosocial, sexual behavior and partner characteristics noted below with PrEP uptake and adherence.

*Primary Covariates and Potential Confounders:*

*Behavioral and Contextual Factors (both cohorts)  
demographic, psychosocial, sexual behavior and partner characteristics*

- Sociodemographic characteristics
  - Current living situation
  - Household composition
  - Private space for product storage
- HIV risk perception for mother and infant
- HIV stigma
- PrEP stigma
- Sexual behaviors
- Substance use
- Mental health and post-traumatic stress symptoms
- Disclosure to peers, family members, teachers, and partner(s) about PrEP use and participation in the study
- Gender-based violence (GBV)
- Partnership characteristics: partner's HIV status

To evaluate factors associated with PrEP use, a similar approach will be used, but analyses will be restricted to Cohort 1 with the binary indicator of "optimal adherence" (based on TFV-DP levels) as the outcome.

To complement both exploratory analyses described above, key themes will be summarized from the qualitative data regarding how aspects of PrEP, women's perception of risk, the context of pregnancy, and interpersonal and structural influences contribute to PrEP uptake, use, and discontinuation. Additional details regarding the qualitative data analysis are at the end of this analysis section.

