#### **4.5 Recruitment, Screening, and Enrollment Process**

Sites will be responsible for developing appropriate recruitment processes that are geared toward their respective local communities. Recruitment materials should undergo approval, if applicable, per institutional review board (IRB)/Ethics Committee (EC) policies and procedures.

Women at heightened risk of HIV acquisition will be recruited for the PK Component and PrEP Comparison Component from public health centers where standard of care HIV pre- and post-test counseling procedures include a standardized HIV risk assessment. Study staff will approach women who, based on this risk assessment, perceive themselves to be at heightened risk and express interest in learning more about methods to protect themselves. After introducing the study, study staff will invite women who express potential interest in the study to initiate the informed consent process; those who provide informed consent will then initiate the study screening process. Women who do not express potential interest in the study will be referred to standard of care HIV prevention services.

All sites are eligible to participate in the PK Component; however, some may elect to opt out. It is also possible that not all sites will be needed to reach full accrual for this component. It is anticipated that all sites will participate in the PrEP Comparison Component.

The IMPAACT Data Management Center (DMC) Subject Enrollment System (SES) will be used to assist with tracking the screening and enrollment process for both the PK Component and PrEP

Comparison Component. When informed consent is obtained, participant identification numbers (PIDs) will be assigned to the mother and infant and a study-specific screening number will be obtained for the mother-infant pair through the SES. For pairs found to be eligible, enrollment will occur upon successful entry of required eligibility data into the SES. For pairs who are found to be ineligible for the study, or who do not enroll in the study for any reason, an eCRF will be entered to record the screening outcome. Refer to [Section 9.3](#) for more information on monitoring participant accrual in this study.

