### 9.2.4 Sample Size and Accrual

The PrEP Comparison Component will enroll a total of 350 (233 in Cohort 1 and 117 in Cohort 2) women over a 12-month period. Women will be followed through 26 weeks postpartum. Expected duration of follow-up for a given maternal participant is between 7 and 12 months depending on the gestational age of the pregnancy at enrollment. The following sample size and power calculations assume a final analysis sample of 300 women (200 in Cohort 1 and 100 in Cohort 2). The primary reason for the 2:1 enrollment into the two cohorts was to balance the need for a “No PrEP” comparison group (to provide the background rates for safety outcome measures) with the need for a large enough PrEP group to examine outcomes that would be restricted to women in that group (Adherence). To achieve this sample size at the analysis phase, this study will enroll ~350 women to accommodate a decrease of ~15% due to maternal attrition.

**Table 8** shows the expected precision of a range of PrEP adherence estimates across different sample sizes in Cohort 1. For example, with a sample size of 200 women in Cohort 1, the width of the 95% confidence interval for an estimated adherence rate of 75% is 13%.

**Table 8: Precision (shown as 2-sided 95% confidence intervals) of different estimates of the proportion with good adherence (for illustration, defined as meeting or exceeding the threshold corresponding to protective drug levels of TFV-DP) at different sample sizes for Cohort 1.**

% Adherent	Sample Size in Cohort 1			
	150	200	250	300
50	42-58%	43-57%	44-56%	44-56%
60	52-68%	53-67%	54-66%	54-66%
65	57-73%	58-72%	59-71%	59-70%
70	62-77%	63-76%	64-76%	65-75%
75	67-82%	68-81%	69-80%	70-80%
80	73-82%	74-85%	75-85%	75-84%

**Table 9** below shows the precision of estimates of safety outcomes (e.g. preterm birth) expected with a range of event rates and a sample size of 200 women in Cohort 1 and 100 women in Cohort 2. It is expected that the rates of these outcomes will be low particularly since this is a young group of healthy HIV uninfected women. To that end, a range of AE rates with corresponding confidence intervals is included in the protocol.

**Table 9: 95% Confidence Intervals for different possible event rates of safety outcomes in Cohort 1 (n=200) and Cohort 2 (n=100)**

Event Rate	95% Confidence Interval	95% Confidence Interval
	Cohort 1 (n=200)	Cohort 2 (n=100)
0.5%	(0, 2.8)	(0, 3.6)
2.0%	(0.5, 5.0)	(0.2, 7.0)
4.0%	(1.7, 7.7)	(1.1, 9.9)

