Stratifying by the above factors in this non-randomized study is for the purpose of monitoring the accrual to ensure that there are not large differences between the two cohorts (PrEP and No PrEP) in the proportion of women who are 16-17 years old, who are from a specific country, or who enroll in the 1st or 2nd (vs. 3rd) trimester of pregnancy, and to ensure a proportion of enrolled women are in the 16-17 year old age group. The team will be closely monitoring and adjusting enrollment to ensure this balance.

The primary analysis for this study will take place after follow-up of all participants in the study has concluded.

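### The PrEP-uptake models do not account for enrollment control that acts on the same outcome: associations with country, age group and trimester may be attenuated, and site-varying predictors biased.

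*Protocol*

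**What the plan says.** Two places in Protocol 9.2.6 plan the analysis. The descriptive summaries state: "Logistic regression models will be fit to identify predictors of PrEP initiation". Other Objective 2.4.1 states: "Women in both cohorts (Cohort 1 and Cohort 2) will be included in analyses of predictors of PrEP uptake at enrollment". It then specifies univariate and multivariate logistic regression on baseline demographic, psychosocial, behavioral and partner characteristics.

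Enrollment by cohort is controlled elsewhere:

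- **Size.** Protocol 9.2.4: "The PrEP Comparison Component will enroll a total of 350 (233 in Cohort 1 and 117 in Cohort 2) women over a 12-month period". The ratio was chosen to balance the need for a comparison group against precision in the PrEP group.
- **Balance.** Protocol 9.2.3 stratifies enrollment by cohort, trimester, country and age group (16-17 versus 18 and over), to avoid large differences between the cohorts.
- **Enforcement.** Protocol 9.2.5 has balance watched at each site. If there is significant divergence it allows "remedial measures, which may include curtailing enrollment to the Cohort more commonly chosen while enrollment into the other Cohort proceeds". SAP 2.1.2 is firmer: "The team will be closely monitoring and adjusting enrollment to ensure this balance".

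The covariate list under Other Objective 2.4.1 names neither country, site nor trimester. Age can enter only through the general demographic heading. Neither statement of the model mentions the enrollment control.

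**The concern.** Cohort is the woman's own decision and is also the dependent variable of the uptake model. Steering who enters each cohort so that the two look alike on country, age group and trimester removes, by design, part of the association between those factors and choice. A finding that uptake does not differ between 16-17-year-olds and older women could then reflect recruitment control, yet be read as evidence about adolescents.

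There is a second route. If one site curtails acceptors and another does not, the acceptor-to-decliner ratio differs by site for reasons unrelated to choice. Any listed predictor whose prevalence also differs by site then picks up a spurious association when site is not in the model.

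Identifying barriers to and facilitators of uptake is a named objective (Protocol 2.4.1), and feasibility and acceptability are the component's purpose.

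**Working it through.** **1. The plan's own split.** Inputs from Protocol 9.2.4: 300 evaluable (200 + 100) and about 15% attrition. N/(1 - 0.15) gives 300/0.85 = 353, 200/0.85 = 236 and 100/0.85 = 118, against the stated 350, 233 and 117. The figures reproduce to within 3 women (350 × 2/3 = 233.3; implied attrition 50/350 = 14.3%). The acceptor share is 233/350 = 66.6%, set by target.

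**2. Does the 2:1 target bias odds ratios?** No. Sampling on the outcome changes only the intercept of a logistic model. A simulation of 400,000 women per scenario (all effects assumed) set true uptake at 34%, 65% or 88%. The 2:1 sample showed 66.7% acceptors each time, so uptake cannot be read from cohort sizes. The adjusted odds ratios came back intact:

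| Factor | Assumed true OR | 2:1 target only | 2:1 plus exact balance |
|---|---|---|---|
| Country | 2.5 | 2.47-2.51 | 0.84-0.85 |
| Age group | 0.5 | 0.49-0.51 | 0.97-0.98 |
| Trimester | 0.6 | 0.60 | 0.98-0.99 |
| Stigma | 0.5 | 0.50 | 0.50 |
| Private storage | 2.0 | 2.01-2.04 | 1.99-2.04 |

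**3. Effect of balancing.** Under exact balance within country × age × trimester (last column), univariate odds ratios for the three balanced factors are 1.00, and their adjusted values have no interpretation. The unbalanced factors are unharmed. Private storage, which varied by country in the simulation, shifts slightly (1.91-1.94) if the balanced factors are left out of the model.

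**4. Partial balance (assumed inputs).** Take 1,000 women, 20% aged 16-17, with uptake 80% in older and 50% in younger women.

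- Older: 640 accept, 160 decline. Younger: 100 accept, 100 decline. True OR = (640/160)/(100/100) = 4.0.
- The younger share is 100/740 = 13.5% of acceptors and 100/260 = 38.5% of decliners.
- If steering lowers the decliner share to 25%, OR = (0.25/0.75)/(100/640) = 0.333/0.156 = 2.1.
- If the shares are equal, OR = 1.0.

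**5. Uneven curtailment (assumed inputs).** Take two sites of 100 women each, with true uptake 80% at both. A predictor has no effect on choice and has prevalence 70% at site A and 25% at site B. Site B stays at 80:20, giving acceptors 20 with and 60 without the predictor, and decliners 5 and 15. Pooling both sites:

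| Site A accept:decline | Acceptors with/without | Decliners with/without | Pooled OR |
|---|---|---|---|
| 80:20 (uncurtailed) | 76/84 | 19/21 | 1.00 |
| 70:30 | 69/81 | 26/24 | 0.79 |
| 60:40 | 62/78 | 33/27 | 0.65 |
| 50:50 | 55/75 | 40/30 | 0.55 |

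Last row: (55 × 30)/(75 × 40) = 1650/3000 = 0.55. If site B is the one curtailed to 50:50 instead, OR = (68.5 × 43.5)/(61.5 × 26.5) = 1.83. Within each site the OR is 1.0 throughout, so conditioning on site removes the bias.

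**6. Scale.** With 200 versus 100 women, two-sided alpha 0.05 and 80% power, the detectable OR for a binary predictor is about 2.7, 2.2, 2.05 and 2.0 at decliner prevalence 10%, 20%, 30% and 50% (prevalences assumed). A spurious 0.55 (inverse 1.82) or 1.83 is only a little smaller than the effects the analysis can detect.

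**The case against.** The strongest reply is that most of the planned analysis is sound. The 2:1 target does no harm to odds ratios. The listed barriers (living situation, storage, stigma, risk perception, mental health, violence, partner status) are not the balanced factors and survive even exact balancing. Balance means avoiding large differences, and curtailment is optional, so attenuation may be small or absent. The analysis is called exploratory, SAP 1.1 sends other objectives to a separate plan not available here, and the qualitative interviews address the same objective. All of this stands, and it limits the point.

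It does not dispose of it. Age falls within the demographic characteristics, and the descriptive summaries cover entry pregnancy characteristics as well. The protection given by outcome-based sampling also requires that, within acceptors and within decliners, selection not depend on anything correlated with the predictors and omitted from the model. Site-specific curtailment breaks that condition, and no adjustment for site is specified.

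Two stronger readings are tempting. A reader might infer that predictors of uptake cannot be estimated at all; the second step of the working shows otherwise. A reader might also infer that the plan will report 67% uptake as a result, but no uptake percentage is planned in Protocol 9.2.6 or listed in SAP section 7.

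**Conclusion.** The concern holds in limited form. Enrollment control acts on the outcome of the uptake models, and the planned models ignore it.

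- **Balanced factors** (country, age group, trimester): odds ratios are attenuated by an unknown amount, from none if enrollment is never adjusted to complete under exact balance. A ratio of exactly 1.0 whatever the truth is the extreme case, not the stated design.
- **Other listed predictors:** estimable. They are at risk only if curtailment differs by site or period and the model omits these. The illustrated bias runs from 1.00 to 0.55, or to 1.83 in the other direction, depending on which site is curtailed and how far.
- **Uptake level:** cannot be inferred from cohort sizes.

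The age-group and two-site figures rest on assumed uptake, prevalence and curtailment, since the documents give none. Whether curtailment took place is not stated. The later analysis plan may already contain the adjustment; the protocol and this SAP do not.

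**What to change.** 1. In Protocol 9.2.6 (descriptive summaries and Other Objective 2.4.1), or in the separate plan for other objectives, fit the uptake and initiation models conditional on country or site, age group, trimester and calendar period of cohort opening, by stratification or adjustment.
2. State that coefficients for those factors will not be interpreted as predictors of uptake, and that cohort sizes do not estimate uptake.
3. Log the dates and sites of any curtailment, so that the conditioning can be done, or a sensitivity analysis restricted to uncurtailed periods.

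Items 1 and 2 are wording. Item 3 is a short log that should be kept during accrual. The statistical cost is slightly wider intervals and no reported effect for the balanced factors. Women enrolled while one cohort at their site was fully closed add no information within their own site-period stratum, so long closures would cost more.

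Adding PrEP choice to the screening form would not replace this. Protocol 4.5 already says that for consented pairs who do not enroll "an eCRF will be entered to record the screening outcome". But the self-interview supplying most predictors is first given at the Entry visit (Protocol 6.2.1.1), and women not interested in the study are referred elsewhere before consent. Such a field could record choices among screened women, but could not support predictor models for all of them.
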